### JHM IRB - eForm A – Protocol

- Use the section headings to write the JHM IRB eForm A, inserting the appropriate material in each. If a section is not applicable, leave heading in and insert N/A.
- When submitting JHM IRB eForm A (new or revised), enter the date submitted to the field at the top of JHM IRB eForm A.

\*\*\*\*\*

#### 1. Abstract

- a. Provide no more than a one page research abstract briefly stating the problem, the research hypothesis, and the importance of the research.

Abuse of opioids is a significant national health problem. Pharmacogenetics, or personalized medicine, uses genotype information to predict phenotypic response (generally medication efficacy or safety). The field of substance abuse is critically lagging behind in the application of pharmacogenetics for identifying individuals at increased risk for developing an opioid abuse disorder, or using personal genetic information to guide treatment. There is growing evidence to suggest a functional polymorphism (A118G) in the OPRM1 gene that codes for the mu opioid receptor (MOR) mediates individual response to opioid medications and has direct relevance for the development of opioid dependence. To date, no controlled human laboratory studies have examined the effect of the A118G SNP or OPRM1 gene on individual response to opioids. The next logical step is to evaluate whether differences in OPRM1 single nucleotide polymorphisms (SNPs) drive individual response to opioid medications, which will help advance the field of substance abuse towards a pharmacogenetics approach to treatment, and establish a precedent for using controlled and well-validated laboratory methodology to investigate the genotype-phenotype interactions of opioids. We are proposing to conduct a laboratory study to evaluate whether the A118G SNP and additional OPRM1 tagging SNPs are associated with a variety of different MOR-mediated functions by evaluating subjective and physiological response to double-blind administration of an opioid medication. We will also evaluate the contribution of OPRM1 on other complex phenotypes related to the MOR activity or opioid dependence (e.g., pain sensitivity, the endogenous opioid-mediated cortisol stress response, and a delay discounting behavioral economic task). This study will be a between-group evaluation of genotype and sex, and a within-subject evaluation of opioid dose-response that will be conducted over 5 days in a residential clinical research unit. Study completers (n=100) will receive double-blind doses of oral hydromorphone or placebo in a randomized, counter-balanced research design. Self-report, physiological, and salivary cortisol measures of drug effects will be collected at several time points following drug administration, and delay discounting will be administered at screening and during peak drug effects. We will also administer different operant pain tasks that provide quantifiable estimates of pain sensitivity, under conditions of placebo or hydromorphone administration. This study will be the most controlled, rigorous, comprehensive examination of the A118G SNP and OPRM1 gene with opioid-mediated effects to date. We expect that genotype will be associated with several opioid-mediated effects, and that the results will advance our understanding of the contribution of OPRM1 to specific behavioral phenotypes. These data will advance the use of pharmacogenetics for substance abuse and use of laboratory testing for genotype-based hypotheses, and will contribute to the development of opioid dependence prevention strategies and interventions to treat comorbid pain and opioid dependence.

#### 2. Objectives (include all primary and secondary objectives).

The primary aim of this study is to examine the associations of specific polymorphisms in the OPRM1 gene with mu opioid receptor (MOR)-mediated effects. We hypothesize the minor A118G SNP allele and OPRM1 tagging SNPs will predict more reinforcing properties of hydromorphone, (e.g., higher self-report ratings of high and drug-liking) and greater opioid-induced physiological changes (e.g., pupil diameter, blood pressure), decreases in cortisol levels as a function of the degree of pleasant effects of hydromorphone, and steeper discounting curves on a delay-discounting task. The secondary aim of this study is to examine the associations of specific polymorphisms in the OPRM1 gene with laboratory measures of pain. We hypothesize the minor A118G SNP allele and OPRM1 tagging

SNPs will predict higher pain threshold on two experimentally-induced laboratory measures of pain, lower analgesic efficacy in response to experimentally-induced pain, and lower cortisol response to painful stimuli. Finally, as an exploratory aim, we will examine the contribution of sex to the primary and secondary aims.

**3. Background** (briefly describe pre-clinical and clinical data, current experience with procedures, drug or device, and any other relevant information to justify the research)

Abuse of opioids has resulted in a 57% and 717% increase in treatment admissions between 1992-2008 for heroin and prescription opioids, respectively (1). Opioid dependence is a chronic, relapsing disorder that is associated with greater health care services, more emergency room visits, prolonged disability, missed work days, and frequent overdose, resulting in an annual societal cost of more than \$8 billion (8 fold greater than nonabusers; (2, 3). Laboratory evaluations of opioids medications reveal robust and consistent between-person differences in self-report and physiological response to opioids (4-8), however no persistent demographic, drug use, and/or treatment characteristics have been identified that reliably predict susceptibility to develop opioid dependence (9-15). The phenomenon of varied individual response to drugs is not limited to opioid medications and clinically causes reductions in efficacy of medications and increased side effect profiles (16, 17). Pharmacogenetics, one approach to personalized medicine, addresses this phenomenon by using genotype information to predict phenotypic response (generally medication efficacy or safety; (18, 19). Regarding opioids, there is growing evidence to suggest a functional polymorphism in the OPRM1 gene that codes for the mu opioid receptor (MOR) may mediate individual response to opioid medications and have direct relevance for the development of opioid dependence (20-25). The most commonly researched single nucleotide polymorphism (SNP) of the MOR is a nucleotide exchange in exon 1 at the 118 position of the N-terminal domain (26), which results in an amino acid change from asparagine to aspartate at position 118 (Asn40Asp or A118G, rs1799971).

We were the first group to show that the A118G SNP of the OPRM1 gene has functional consequences on human behavior (27). Human laboratory studies have reported a reliable and robust, endogenously-mediated cortisol response to the opioid antagonist naloxone (27-32), a greater adrenocorticotrophic hormone stress response (29), and decreased pupillary constriction (33-35) in response to opioid administration. Laboratory studies examining alcohol and nicotine have reported functional associations between the A118G SNP of the OPRM1 and behavioral outcomes such as increases in striatal dopamine following nicotine exposure (36), decreased cerebral blood flow following nicotine abstinence (37), increased MOR binding potential (38) and MOR availability (39), finding smoking more reinforcing (40, 41), and greater sensitivity to alcohol. Most recently we have identified that the minor allele predicts lower D2/D3 receptor binding potential in the nucleus accumbens ([name] and co-workers, editorial review in preparation). Altogether, these data are now being used to predict clinical differences in treatment response based on OPRM1 status, such as efficacy of naltrexone for alcohol treatment (42, 43), nicotine replacement products for nicotine (44, 45), and severity of nicotine withdrawal symptoms (46). The field of medicine has embraced the promise of pharmacogenetics more broadly and has published several studies that use genotype to guide treatment for alcohol (47), breast cancer (48), hepatitis C (49), warfarin (see (50)), leukemia (51), AIDS (52), P450 enzymes (53), psychotropic medications (54), and pain (55). This approach has great potential because it prevents physicians from prescribing medications that have a lower likelihood of working or are unsafe within different genetic subgroups, ultimately increasing efficiency, reducing time to positive therapeutic response, and minimizing potential side effects of medications. Patients also support the use of genetics to guide prescribing (56).

The field of substance abuse is critically lagging behind in the application of pharmacogenetics for identifying individuals at increased risk for developing an opioid abuse disorder, as well as using personal genetic information for tailoring treatment decisions. The majority of studies that have evaluated the contribution of the OPRM1 gene to human behavior are either Genome Wide Association Studies (GWAS) that provided self-report surveys to large patient samples and looked for associations, or retrospective chart reviews that collected genetic information from clinical patient populations who received opioid medications for pain (21, 57-66). The primary pitfalls of these approaches are that the phenotype (e.g., substance abuse) is either poorly defined or unreliably measured. The field of genetics has begun moving away from these association models; they do not yield consistent results because the measures used to define the phenotype are very heterogeneous across studies and are ultimately poor representations of the target phenotypes. Two independent reviews have recently argued that controlled laboratory examinations of endophenotypes that are evaluated under rigorous experimental conditions better approximate the complex phenotype of drug dependence and produce stronger effect sizes than large-scale association studies that rely on retrospective self-report (67, 68).

To date, no controlled human laboratory studies have examined the effect of the A118G SNP or the larger OPRM1 gene on individual response to opioids. The proposed laboratory study is a necessary first step to evaluate

whether differences in OPRM1 single nucleotide polymorphisms (SNPs) drive individual response to opioid medications, which will help advance the field of substance abuse towards a pharmacogenetics approach to treatment, and establish a precedent for using controlled, reliable, and well-validated laboratory methodology to investigate the genotype-phenotype interactions of opioids. Laboratory studies are ideal for targeting specific behavioral phenotypes because they are rigorously controlled, permit within-subject evaluations of drug effects and double-blind dose administration, identify dose-graded effects, target well-established and specific phenotypes of drug use behavior that can be directly compared to existing literature to guide interpretation of effects, permit cross-laboratory and cross-species comparisons and replication of effects, are robust and reliable predictors of clinical outcomes, and produce larger effect sizes than GWAS studies (67, 68). Our group has specific expertise in conducting laboratory assessments of opioid effects using a model that is considered the standard by the Food and Drug Administration, industry, and national organizations (69). Thus, we are proposing to conduct a laboratory study to evaluate whether the A118G SNP and additional OPRM1 tagging SNPs are associated with a variety of different MOR-mediated functions by evaluating subjective and physiological response to double-blind administration of an opioid medication, pain sensitivity and response to medications for pain (secondary aim, beginning Page 9), the endogenous opioid-mediated cortisol stress response, and a delay discounting behavioral economic task that has been reliably associated with the drug abusing phenotype. This study will advance our understanding of the contribution of genotype to abuse liability, pain, endogenous stress response, and delay discounting. These data can be used to modify analgesic doses and treatments, reduce potential for side effects from opioid medications, predict susceptibility to opioid dependence (70, 71) and develop innovative intervention strategies, and advance the use of controlled laboratory testing to evaluate genotype-based hypotheses. This study will also provide a unique opportunity to identify whether these effects are evident among people that demonstrate increased abuse potential for opioids prior to the development of opioid dependence.

There is also substantial individual variation in the subjective response to nociceptive (e.g., painful) stimuli. Genetic factors have been shown to contribute to that variation (72-75) and growing evidence indicates the functional action of the OPRM1 may influence the associated endogenous opioid response (mediated by beta-endorphin) to pain (26, 76). Several studies report that the minor allele of the A118G may confer a resistance to nociceptive (e.g., painful) stimuli. First, carriers of the minor allele have lower beta-endorphin-mediated serum concentrations of circulating proinflammatory cytokines (77), and a robust beta-endorphin mediated increase in cortisol release following naloxone administration (27-32). Second, controlled human experimental studies report higher pain thresholds in minor allele carriers (78-81), and a longitudinal cohort study reported higher positive affect across 30 days of repeated measurement among A118G minor allele variants with the chronic pain disorder fibromyalgia (82), which is consistent with preclinical studies that reported increased pain sensitivity following direct administration of beta-endorphin (83, 84). The minor allele of the A118G has also been consistently associated with increased medication requirements to achieve analgesia. For example, preclinical and human laboratory studies report that A118G minor allele carriers experience less relief from opioid agonists (85-87), and several retrospective chart reviews report greater postoperative medication requirements (35, 88-96).

[figure not shown]
Additional, well-controlled studies are needed to understand and advance our knowledge regarding the effect of the A118G SNP and additional OPRM1 tagging SNP variants on baseline pain tolerance, and pain tolerance under conditions of opioid analgesic treatment. Only two studies have examined the contribution of the A118G on pain tolerance in controlled laboratory settings (78, 81). The first study reported positive associations between A118G and pain on two of the three pain tolerance tests conducted, but did not evaluate tolerance to pain following opioid agonist administration (78, 81). The second study reported a positive association with OPRM1 on one test of pain following oxycodone administration, but did not evaluate additional pain tolerance tests, which is important given the high rate of individual variability among pain testing methods (78, 81). Neither study sampled across the OPRM1 gene and or was designed to prospectively evaluate gender, which is critical because of the robust gender-specific effect that exists on pain and its potential interaction with the OPRM1 gene (41). The current study will extend upon these studies by evaluating the effect of the A118G SNP and OPRM1 gene using a quantitative sensory testing (QST) paradigm, under conditions of double-blind and placebo-controlled hydromorphone administration, and will conduct gender specific analyses. Women will only be enrolled during the first two weeks of their cycle (confirmed via progesterone analysis) to minimize hormonal effects on pain, which will be the most rigorous evaluation of OPRM1 and pain within gender to date. Further, one of our pain tests will activate the diffuse noxious inhibitory control (DNIC) system, which is mediated by the endogenous opioid system, hypothesized to be a model of chronic pain, and believed to contribute to opioid-induced hyperalgesia (97). No prior study has used the DNIC procedure to evaluate OPRM1 effects on pain tolerance, which is critical because of the established functional relationship between the OPRM1 and the endogenous opioid response (26, 98). The results will advance our understanding of the OPRM1 contribution to pain tolerance and response to medication, help elucidate the

mechanism behind opioid-induced hyperalgesia, and may be used clinically to guide development of chronic pain interventions and prescribing guidelines. These results will also be compared to abuse liability outcomes, which- to our knowledge- will be the first within-person comparison of opioid abuse liability and pain effects as a function of genotype.

#### 4. Study Procedures

- a. Study design, including the sequence and timing of study procedures (distinguish research procedures from those that are part of routine care).

**Study Overview:** This study will be a between-group (total completer N=100) evaluation of genotype and sex, and a within-subject evaluation of opioid dose-response. The study will be conducted over 5 days (4 nights) at the Behavioral Pharmacology Research Unit (BPRU) and a residential clinical research unit (CRU) (Figure 1). Day 1 will be an Admission day. Days 2-5 will consist of blinded study drug administration in the morning, 1 pain testing session, and self-report/physiological measures of drug effects for 6 hours post dosing. Participants will receive double-blind doses of oral hydromorphone (2mg, 4mg, 8mg) (99-102) or weight and color-matched placebo in a randomized, counter-balanced research design.

**Screening Visit:** Participants will complete a brief phone screen to determine initial eligibility and will be invited to complete an in-clinic screen. Participants will sign an informed consent form with a study staff member to begin the Screening visit. To reduce expectancy effects, the consent will inform participants the study drug may consist of one or more of numerous different drug classes (e.g., opioids, stimulants, over-the-counter medications), a common practice in laboratory based studies of drug effects (103, 104). Following consent, a staff member will administer a battery of measures to establish study eligibility (see Study Measures below). A urine sample will be collected and tested for evidence of illicit drugs and to establish medical eligibility. A blood sample of no more than 2 tablespoons will also be collected from eligible participants for medical and genotype analysis. Participants will also be asked to provide a second blood sample (2 additional tablespoons) that will be collected at either Screening or Admission and stored for future genetic analysis. This will be voluntary. Participants who meet eligibility criteria (including results of laboratory blood tests) will be scheduled for an Admission day.

**Study Day 1, Admission Visit:** Participants will complete a brief history and physical to determine final study eligibility and will be admitted to the CRU for 5 days (Admission day + 4 session days). During the Admission day, participants will be familiarized with the pain testing procedures and the measures used during session days 2-5.

**Study Days 2-5, Session Days:** The morning of each session, participants will be provided with a standardized breakfast, and cigarette smokers will be permitted 1 cigarette the morning prior to a session (1 additional cigarette will be permitted every 2 hours during the session). Sessions may take place either at the CRU or the BPRU, however all participants will reside overnight in the CRU. Participants will receive a standardized lunch and dinner. Beginning on Day 2, participants will receive a blinded study drug in the morning, will conduct a pain testing session approximately 60-90 minutes post-dose, and will provide self-report, observer-ratings, and physiological measures of drug effects for an additional 6-hours post-dosing. Each element is described in more detail below. Participants will also provide a blood sample (no more than 1 tablespoon) that will be analyzed for metabolic status. This sample can be collected at any point during Study Days 2-5.

**Pain Testing:** Participants will undergo 1 pain-testing session each day. Sessions will consist of pressure pain threshold, conditioned pain modulation, and temporal summation testing. Participants will be oriented to the study measures and pain testing apparatuses during the Admission Day. During the sessions, study drug will be administered under double-blind conditions in the morning. Salivary cortisol samples will be collected following completion of the pain testing session to evaluate the acute stress response to each pain stimulus, as a function of

drug (placebo vs. hydromorphone). Ratings of numeric rating scales will be used for data analysis, and participants will be asked to identify whether a placebo or active drug had been administered.

**Pressure Pain Threshold:** The pressure pain threshold is defined as the kilopascals (kPA) value at which a mechanical stimulus is first judged to be painful. An electronic algometer with a 1cm^2 hard rubber probe will be applied two times to two different muscle groups in randomized order. Pressure will be applied at a constant rate of 30kPA/s until the participant first reports pain. A 30 second interval will be imposed between each stimulus presentation (105). The values in kPA will be averaged across administrations and muscle groups to create an index of pressure pain threshold. Administering the stimulus at multiple anatomic locations increases the reliability of the pressure pain threshold. Possible effects of laterality and muscle group will be evaluated to determine if threshold outcome measures should be separated into subgroups.

**Conditioned Pain Modulation:** We will also conduct a test of conditioned pain modulation, formerly known as diffuse noxious inhibitory controls. Conditioned pain modulation is the process by which the pain induced by a tonic conditioning stimulus inhibits the pain produced by another noxious stimulus at a distal anatomic location. This procedure initiates a robust activation of the endogenous opioid system that is attenuable by administration of naltrexone (106). Our conditioned pain modulation procedure will measure the change in pressure pain threshold at the trapezius muscle induced by immersion of the contralateral hand in cold water. Two baseline pressure pain threshold readings will be assessed via algometry. Participants will then immerse their hand in a circulating ice water bath maintained at 10 +/- 1 °C and will not be told the duration of time for which their hand will be submerged. After 20 seconds, with their hand still submerged, participants will rate their pain on a 0-100 numeric rating scale (NRS; (107), where 0=No Pain and 100=Is Worst Pain Imaginable, and after 45 seconds participants will be asked to remove their hand from the water bath. Simultaneously with hand withdrawal, an algometer will be applied and pressure pain threshold in kPA will be recorded. This procedure will be repeated contralaterally after a 5-minute interval. The order of administration with respect to laterality will be randomized. Conditioned pain modulation will be indexed as the percent change in pressure pain threshold from the baseline administration to the conditioned administration, averaged across the 2 trials (105). Conditioned pain modulation can be conducted with a variety of heterotopic conditioning stimuli, including thermal, ischemic, and electrical stimuli. Cold-water immersion (also known as the cold pressor test) is an attractive choice for the conditioning stimulus because noxious cold stimuli activate cutaneous A $\delta$  and C fibers, resulting in rapid nociceptive neurotransmission (108). This conditioned pain modulation method has been selected for this study because it has been independently validated as a sensitive and reliable measure of descending pain inhibition (109), and it activates the endogenous system that is hypothesized to be altered by the OPRM1 gene.

**Mechanical Temporal Summation.** Temporal summation of pain will be assessed using repetitive mechanical stimuli. The assessment of temporal summation involves rapidly applying a series of identical noxious stimuli and determining the increase in pain across trials; animal studies have suggested that temporal summation occurs centrally in second-order neurons in the spinal cord as a consequence of sustained C-fiber afferent input (149-151). For temporal summation of mechanical pain, pain ratings in response to a single punctate noxious stimulus will be compared to pain ratings in response to a sequence of identical punctate noxious stimuli (152). A weighted pinprick stimulator with a flat contact area will be used to deliver either a single pinprick stimulus or a train of 10 pinprick stimuli repeated at a constant rate. Following the single stimulus and the 10-stimulus train, the subject is asked to give a pain rating. Single pinprick stimuli are alternated with the trains of 10 stimuli. Similar procedures using this type of weighted pinprick stimulator have been used in diabetic neuropathy (153), healthy subjects (154), and to assess temporal summation (155-156).

**Acute Effects of Hydromorphone:** Participants will ingest medication under staff supervision and complete a battery of self-report, physiological, and cortisol measures will be collected prior to dosing and up to 15 time points post-dose (up to 6 hours). During the final assessment each day, participants will complete a Drug vs. Money Questionnaire modeled from the Multiple Choice Procedure to indicate the dollar value they would place upon the drug received and this measure will be repeated immediately prior to the next day's drug administration. These experimental procedures are consistent with those used in a previous study by our group (110). Participants will be discharged from the study on the final day after completing the final study assessment and a field sobriety test that indicates no persistent opioid effects. We will conduct a follow-up phone call with participants the day following discharge to document any adverse events and to administer the final Drug vs. Money Questionnaire.

**General Study Assessments:** We have included several measures during the Screening visit to enable us to characterize the population and collect preliminary information that might differentiate between genetic groups or be used to support future research applications, including a questionnaire to evaluate domains the NIDA Genetic

Council recommends be documented in genetic studies. The measures comprise both pharmacologically and qualitatively nonspecific measures (e.g., any drug effect) and qualitatively specific measures (e.g., liking, good effects, bad effects, nausea), which have been recently recommended by a consensus panel and the FDA. OPRM1 has recently been associated with negative side effects of opioid medications so we will specifically assess negative symptoms and side effects following drug administration.

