## 7. Study Statistics

a. Primary outcome variables. The primary outcome variables are self-reported ratings of drug high and liking, changes in pupil diameter and blood pressure, pain threshold on 2 laboratory measures of pain, and analgesic efficacy in response to laboratory-induced pain. We expect that individuals with the minor allele of the A118G SNP and other

tagging SNPs across the OPRM1 gene will find hydromorphone more reinforcing (e.g., higher self-report ratings of high and drug-liking) and exhibit greater opioid-induced physiological changes (e.g., pupil diameter, blood pressure). Research also suggests the OPRM1 gene may also confer greater sensitivity to the negative effects of opioids, which may be observed as measuring greater ratings of nausea. We also hypothesize the minor allele and other tagging SNPs across the OPRM1 gene will produce higher pain threshold on 2 laboratory measures of pain, and lower analgesic efficacy in response to laboratory induced pain.

**b. Secondary outcome variables.** Decreases in cortisol levels as a function of the degree of pleasant effects of hydromorphone and painful stimuli, delay-discounting curves, and the effect of sex on all outcome measures. We hypothesize that individuals with the minor alleles will have greater decreases in cortisol levels as a function of the degree of pleasant effects of hydromorphone, lower cortisol in response to painful stimuli, and steeper discounting curves on a delay-discounting task. Finally, although we expect that the A118G will be associated with these effects, we hypothesize that several of the additional OPRM1 tagging SNPs will contribute to effect magnitude.

**c. Statistical plan including sample size justification and interim data analysis:** The aims of the proposed study will explore the impact of genetic variation across the OPRM1 gene on hydromorphone response. There are specific steps we describe below to assure that we interrogate all known functional variation across the OPRM1 gene, adequately cover all other variation using appropriately selected tagging SNPs, prevent spurious associations due to population stratification by accounting for local ancestry, and properly control the Type I error rate.

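### Cortisol taken after the whole pain session cannot give a response to each stimulus, and without a designated pre-pain sample the separation of pain from drug is not assured

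*Combined protocol and SAP*

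**What the plan says.** Section 4a places pain testing on every dosing day: "Participants will undergo 1 pain-testing session each day". On each of Days 2-5 the participant is dosed in the morning and "will conduct a pain testing session approximately 60-90 minutes post-dose". The content is fixed: "Sessions will consist of pressure pain threshold, conditioned pain modulation, and temporal summation testing". On cortisol the same section says: "Salivary cortisol samples will be collected following completion of the pain testing session to evaluate the acute stress response to each pain stimulus", and the sentence goes on to make this a comparison between placebo and hydromorphone.

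Cortisol is also sampled serially. Under Acute Effects of Hydromorphone, "cortisol measures will be collected prior to dosing and up to 15 time points post-dose (up to 6 hours". The Abstract repeats that "salivary cortisol measures of drug effects will be collected at several time points following drug administration". Section 6a gives each participant one placebo day, within Days 3-5.

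Section 7b expects minor-allele carriers to show "greater decreases in cortisol levels as a function of the degree of pleasant effects of hydromorphone, lower cortisol in response to painful stimuli". Section 2 puts the pleasant-effects part under the primary aim and the pain part under the secondary aim; section 7b lists both as secondary outcomes. The mixed model for the pain sessions in section 7c names pressure pain threshold and two conditioned-pain measures as dependent variables. Cortisol is not among them, although a lower cortisol stress response is hypothesised in the same paragraph.

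**The concern.** The post-session sample is given a task that it cannot do, and a second that it can do only with help. A sample taken after three consecutive tests reflects all three together. It is also taken after dosing, on days when the plan itself expects hydromorphone to lower cortisol. Section 6b puts the plasma peak at 30-60 minutes, just before the pain session. No dosing day omits pain testing, and the text names no cortisol sample as the pre-pain baseline.

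If the post-session value is compared between drug conditions as written, a genotype difference in the direct drug effect could be reported as a difference in the stress response to pain. A pre-pain sample that is not scheduled cannot be recovered later.

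**Working it through.** There is no stated figure to reproduce. The check is which quantities the planned samples can estimate.

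**Inputs.** Four dosing days (placebo and three active doses), each with all three pain tests at about 60-90 minutes (section 4a). Cortisol before dosing and at up to 15 post-dose times (section 4a). One placebo day (section 6a). A sample just before pain testing is an assumption, because the text gives no clock times.

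**Notation, within one genotype group.** B is the basal level and T the time-of-day trend since the pre-dose sample. D is the direct drug effect, P the cortisol response to the pain session without drug, and I the change that the drug makes to that response. Subscript 1 means just before pain testing, subscript 2 after the session.

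| Sample | Placebo day | Active day |
|---|---|---|
| Pre-dose | B | B |
| Just before pain (assumed) | B + T1 | B + T1 + D1 |
| After session | B + T2 + P | B + T2 + D2 + P + I |

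**1. Single stimuli.** P is the sum of three parts, one per test, and all three enter every post-session sample together. I checked this by matrix rank with 7 parameters (intercept, three doses, three tests); a contrast is estimable if adding it to the design leaves the rank unchanged.
- Post-session samples only: rank 4 of 7. Drug against placebo is estimable; total pain and single tests are not.
- Pre-dose plus post-session, no time trend: rank 5 of 7. Drug and total pain are estimable; single tests are not.
- Pre-dose, pre-pain and post-session, no time trend: rank 5 of 7, with the same result.

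So 0 of 3 single-stimulus responses are identifiable under any of these schemes.

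**2. The stated drug contrast.** Active minus placebo after the session is (B + T2 + D2 + P + I) - (B + T2 + P) = D2 + I. The drug-free response P cancels. What remains is the direct drug effect plus the drug-by-pain effect, and the two cannot be split. With free time effects and a drug effect that changes over time, the rank check agrees: only the sum D2 + I is estimable after pain.

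**3. Placebo-day level without an anchor.** The genotype difference, written with the prefix Δ, is ΔB + ΔT2 + ΔP. A basal difference is not removed.

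**4. Placebo-day change from a pre-pain sample.** The change is (T2 - T1) + P, so the average pain response is still mixed with time of day. The genotype difference is Δ(T2 - T1) + ΔP, which equals ΔP if the trend over that interval does not differ by genotype. The pre-dose sample could serve as anchor instead, but the trend assumption must then hold over a longer interval that includes the 60-90 minutes before pain testing.

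**5. Active-day change.** Active change minus placebo change is (D2 - D1) + I. This describes the response as modified by drug; it does not isolate I.

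**6. Pleasant-effects curve.** Active minus placebo is D1 before pain and D2 + I after the session. The full placebo-subtracted curve is free of pain effects only if I = 0. Section 7c predicts less hydromorphone analgesia in carriers, so an I that differs by genotype cannot be excluded on the plan's own hypotheses.

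**7. Could a pre-pain sample already be planned?** If all 15 post-dose times were used and evenly spaced, the gap would be 6 × 60 / 15 = 24 minutes, with samples at 24, 48 and 72 minutes. Two would precede a session at 60 minutes and three a session at 90 minutes. Even spacing and full use are assumptions.

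**The case against.** The strongest reply is that the data needed are largely planned. Cortisol is taken before dosing and serially afterwards, and each participant has a placebo day with the same pain session, on which no drug effect exists. This stands. A reader might infer that pain and drug cannot be separated at all; steps 4 and 6 show that they can in part, with samples of the kind already foreseen.

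A reader might also infer that one lower post-pain value in carriers would support both cortisol hypotheses. The documents do not support that. The drug hypothesis ties the cortisol fall to the degree of pleasant effects, and a lower mean after pain does not show that relation.

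It can further be said that no listed aim is lost, because sections 2 and 7b speak of painful stimuli in general and only section 4a promises a response to each one. That is right, and it makes the rewording a matter of bringing section 4a into line. Nor can it be asserted that no pre-pain sample exists: step 7 shows that a full, even schedule would include some, and Figure 1 is not available here. What remains is that the text designates none and defines no cortisol contrast beyond placebo against hydromorphone.

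Finally, restricting the drug hypothesis to pre-pain samples would discard most of the 6-hour curve. That is a fair criticism, and the restriction should not be the main analysis.

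**Conclusion.** The point holds in a limited form. No individual-stimulus cortisol response can be obtained from samples taken after the block (0 of 3). The stated post-session drug contrast estimates D2 + I, which mixes direct drug effect with drug-by-pain effect and contains nothing of the drug-free pain response. Separation of pain from drug is not assured by the text, but it is partly available from the serial samples and the placebo day.

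The size of any misattribution cannot be stated, because the documents give no cortisol means, variances or time course. The placebo-day solution assumes that the time-of-day trend between the two samples does not differ by genotype. How long salivary cortisol lags a stressor is not given in the documents and was not used. This is a cheap improvement to secondary outcomes, one of which section 2 also places under the primary aim.

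**What to change.** 1. In section 4a, schedule one of the up to 15 planned post-dose cortisol samples immediately before pain testing.
2. Define the pain cortisol outcome as the change from that sample to the post-session sample, and enter it in the section 7c analysis.
3. Test the genotype hypothesis for pain on the placebo day, stating the assumption about the time-of-day trend. Report the active days as the drug-modified response.
4. In section 4a, refer to the pain testing session as a whole, in line with sections 2 and 7b.
5. For the pleasant-effects hypothesis, keep the placebo-subtracted full curve as the main analysis and add a sensitivity analysis restricted to samples taken before pain testing.

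The cost is one sample time fixed in advance, some added noise from change scores, and a few lines of text. No additional sample or visit is needed.
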